**Section I. IRB Protocol for All Studies**

Section I is completed for ***all studies*** and includes questions to determine whether the study qualifies for exemption. Section II is only completed if the study does not qualify for exemption.

**1. Hypothesis / Objective / Goals / Aims.**

Briefly describe the study's hypothesis / objectives / goals / aims.

Konzo is a neurological disease associated with chronic reliance on poorly processed cyanogenic cassava as the main source of food. We found that school age children from konzo areas present with poor neurocognition compared to those from nearby non-konzo areas, persisting and worsening even 4 years after initial assessment. Our most recent work has extended these findings to children as young as a year in age, suggesting that the neurodevelopmental impact from cassava cyanide neurotoxicity may begin as soon as children are weaned from breast milk to cassava porridge. The “wetting method (WTM)” is a simple and effective method of detoxifying cassava flour prior to eating that is being taught to rural women in a clinical-trial study by our group in the Democratic Republic of Congo (DRC). The present proposal seeks to combine a curriculum of mediational intervention for sensitizing caregivers (MISC) with a WTM training program (MISC/WTM). MISC is an early childhood development (ECD) caregiver training program previously demonstrated in clinical trials by [name] and colleagues to improve health, neurodevelopmental, and caregiver mental health outcomes in rural Ugandan HIV-affected households. Training 66 randomly selected moms from a cohort of 100 on MISC/WTM (while the remaining 34 get WTM only) will better sensitize mothers to their children’s development, leading to better WTM adherence while providing practical ECD benefits.

The Aims for this study are:

1. To establish the feasibility of adding a biweekly 1-year MISC/WTM training program for mothers and their 1 through 4-year-old children, led by peer trainers from the community. MISC has been previously implemented for HIV-affected households in Uganda, but not for konzo communities in the DRC.

2. To document whether better adherence to WTM through MISC will lead to lower household flour cassava cyanogenic content and lower urinary thiocyanate (U-SCN) levels in the mother/child dyads. We will also test for improved child outcomes on the Fagan Test of Infant Intelligence (with automated eye tracking), Mullen Scales of Learning (MSEL), the Early Childhood Test of attention (ECVT; eye tracking), and the Color-Object Association Test (COAT). Caregiver depression/anxiety and corresponding functionality for activities of daily caregiving should also significantly improve.

3. To explore whether reductions in cyanogenic exposure from cassava and improved child's neurodevelopmental outcomes are mediated by improvements in caregiver emotional wellbeing and caregiving functionality immediately post MISC intervention and at 6-month follow-up. Overall Impact. Our DRC/USA partnerships will be the first to implement an evidence-based ECD program for at-risk children in the DR Congo, strengthening DRC Ministry of Health efforts to prevent konzo. If MISC strengthens the programmatic efforts to prevent konzo, the public health impact will be enormous, given the scope of risk in toxic-cassava dependent populations throughout central/western Africa. MISC could then also be used for children at ECD risk from other infectious diseases.

**PUBLIC HEALTH RELEVANCE:** Early childhood (1 through 4 yrs) is a period of dramatic developmental change that can be seriously compromised by exposure to toxic cyanogenic cassava (konzo disease), with potentially great impact throughout central and western sub-Saharan Africa in regions dependent on this food staple. In the face of ongoing economic instability and nutritional, medical and educational deprivation affecting communities at risk for konzo in the Democratic Republic of Congo, no programs exist for sustaining a favorable developmental milieu for young children. By establishing the viability of caregiver training intervention to enhance functionality among caregivers and improve caregiving quality while preventing konzo, this project can benefit neurodevelopment for tens of millions of at-risk children.

## 2. Procedures.

Describe the research procedures that involve obtaining information or biospecimens about a living person through interaction or intervention and/or by obtaining their identifiable private information or identifiable biospecimens. If subjects will participate in or undergo an intervention, fully describe the intervention. If the procedures are longer than 1 page, provide a summary and include the full procedures as an attachment.

Caregiver/child dyads will be randomized (by cluster) whereby 66 of the 100 households will be selected to randomly receive MISC/WTM caregiver training to enhance caregiver mental health and functionality and early childhood development. The remaining 34 households will receive WTM only (considered the recommended standard of care for the prevention of konzo disease in at risk communities). This is in order to see if adding MISC to caregiver training enhances adherence to WTM for flour detoxification, corresponding child neurodevelopmental and caregiver functionality mental health outcomes – as compared to WTM alone for similar households. To maintain concealment of MISC training allocation, the randomization sequence was generated by the trial biostatistician located in the USA, who also serves as our clinical methodologist and biostatistician for the R01 WTM konzo prevention non-inferiority clinical trial.

The WTM intervention. The intervention will implement the WTM cassava processing technique in participating households. Twenty women with leadership and communication skills have already been trained and are implementing WTM in the R01 trial and will do the training for our WTM-only households in this R21 study. These are mothers who master the WTM technique and have been certified as trainers to train and support other small groups of other mothers. They have to be able to bring the cassava cyanogenic content to the lowest achievable level, which must be < 10 ppm as per the WHO recommendations.

The wetting method to remove cyanogens from cassava flour involves adding dry flour to a bowl and marking the level on the inside of the bowl. Water is then added with mixing, the volume of

the damp flour initially decreases and then increases as more water is added. No more water is added when the level of the wet flour comes up to the mark. The wet flour is then placed in a thin layer not greater than 1 cm thick on a mat and allowed to stand for 2 h in the sun or 5 h in the shade for the hydrogen cyanide gas to escape. The damp flour is mixed with boiling water to make the thick porridge (fufu) which is eaten with pounded, boiled cassava leaves (saka saka) or some other food to give it flavor. Colorfully illustrated and durable laminated posters depicting the WTM will be distributed to participating households as our previous experience indicate that they are kept for more than a year on walls in houses. The WTM approach is our chosen strategy for prevention, because it has been repeatedly demonstrated that it helps remove cyanogens in poorly processed cassava flour to safe levels, even if the flour is initially very toxic due to poor or limited processing.

Mediation Intervention for Sensitizing Caregivers (MISC) Training Intervention. The MISC/WTM trainers will be different from the WTM-only trainers (who will not be certified in MISC). The MISC/WTM training will be led by 10 women leaders in the Kahemba community (different than the WTM peer or professional trainers) who have already been trained by our Uganda MISC consultants in April 2018 and are presently implementing MISC training in Kahemba with 40 households with younger children as part of a pilot study funded by Michigan State University African Alliance Partnership program grant to [name] (<http://aap.isp.msu.edu/research-funding/grant-program/scaling-grants/>). Our two principal Ugandan MISC consultants led the MISC intervention teams in both of [name]'s R34 MH082663 and R01 HD070723 cluster RCT studies, and have already conducted a one-week training workshops with our 10 women leaders and worked with them in the initial adaptation and implementation of MISC in Kahemba for a one-week period (May 2018). The Ugandan MISC trainers will continue to train the community leader women responsible for MISC training at the Kahemba study site for the present R21 study until they are MISC-certified, and continue quality assurance follow-up for fidelity of MISC training in Kahemba every six months throughout the R21 study period. In the present pilot study phase, training session videos of the ten Kahemba community leader woman MISC trainers conducting individual training sessions are planning to upload videotapes of training sessions monthly to a highly secured Dropbox. These will be evaluated by our Uganda MISC expert consultants as part of a quality assurance evaluation for "fidelity of intervention" in Kinshasa and in Kampala Uganda, with the help of a DRC assistant working with us in Kampala and fluent in the local DRC languages of Kikongo and Chobwe

Fidelity of both interventions will be maintained through established methods outlined by the NIH Treatment Fidelity Workgroup on consistency in dose, providers, delivery, and receipt of the intervention

Questionnaires will be administered by an experienced interviewer with local language fluency and overseen by a study coordinator from the Congo Ministry of Health. The questionnaire seeks individual demographic data, occupation (mostly local farming), diet composition (mostly uniform cassava), cassava preparation method (including any changes resulting from prior intervention), 24- hour diet recall (composition, amount and number of meals), smoking history and practice (usually negative), prior family episodes of acute cassava cyanide toxicity (severe headache, vomiting, convulsions, coma, death), and onset date and course of any symptoms of konzo among household members.

All caregivers will complete these questionnaire, undergo on-site neurological screening and urine SCN and provide blood and urine specimens for the biomarker study at baseline, after six-months of caregiver training, and at one-year at the conclusion of the caregiver training period. A sample of cassava flour originating from the subject's household will be collected on the same day prior to urine collection. Trained technicians from the Ministry of Health will measure the cyanogen content of the cassava flour using the picrate kit as in previous studies or interventions.

Children will be evaluated with a battery of non-invasive, performance-based neuropsychological tests at baseline, after six months and at one year after initiating trainings. These evaluations include the Modified Fagan Test of Infant Intelligence, the Mullen Scales of Early Learning, the ZEarly

CHildhood Vigilance Test. Caregivers will respond to the Home Observation for the Measurement of the Environment, the Hopkins Symptoms Checklist-25, and the caregiver functional impairment for daily activities.

Other caregiver/child assessments include video-taping of 15 minutes of child/caregiver interactions (5 minutes of caregiver feeding of child, washing of child, and work or play with child). These videos will be used on tablet as part of the MISC training, but also scored for observed mediational interactions in order to assess fidelity of MISC training and quality of caregiving. These video will be encrypted and password secured and will not be kept after the study, so as not to put the study identity of mothers and their children at risk. Mothers will consent to these videos as part of the informed consent process, and it will be a condition of eligibility for enrollment. This procedure with recording and scoring and management of videos was done for our Uganda-based clinical studies without adverse incidents or problems, and were clearly an important part of this type of caregiver training ECD intervention and assessment in a field-based clinical trial.

*CLICK™ IRB: Upload instruments (e.g. surveys, interview questions, questionnaires, etc.), measures, variables, etc. to the Supporting Documents SmartForm page.*

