on project timeline and resources. With n=66 in MISC+WTM arm and n=34 in WTM only arm. Based on our clinical studies with a biweekly MISC caregiver training with mothers with HIV in rural eastern Uganda, we expect an over 90% retention rate for the full year. With this retention rate, the unadjusted effect size of 0.60 is detectable as statistically significant with power of 0.80 and 0.05 level of significance in two-tailed tests, that is differences between trial arms of 0.6 of the standard deviation or greater will be captured with statistical significance. For the main trial arm effect (differences between arms over time) from two repeated measures at 6 and 12 months with the planned covariance adjustment for baseline, the adjusted standard deviation is smaller than the unadjusted due to the reduction in error variance. Assuming correlation of 0.4 between pairs of repeated measures seen in past testing of MISC, the adjusted detectable effect size is 0.44. This effect size is consistent with past testing of MISC in HIV-affected households that produced effect sizes ranging from 0.35 to 0.53, and is below the threshold of 1/2 of the standard deviation for clinical significance. Thus any meaningful differences between arms will be captured with the proposed sample size. If the differences between trial arms correspond to the adjusted effect size smaller than 0.44, the effect size will be estimated in this study and used to power future clinical trial studies.

**10. Minimal Risk Research.** Complete the following question if you selected an expedited category in Question 8A.

- A.** Briefly describe the background for conducting the research. (1-2 sentences)

- B.** Sample Size.

- i. Provide an estimated sample size for the lifetime of the study at this investigator's sites.

- ii. Describe the basis for that estimate.

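### The detectable effects of 0.60 and 0.44 treat households as independent, although villages are randomised and MISC households share ten trainers who work only in that arm.

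*Combined protocol and SAP*

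**What the plan says.** **Trainers.** Under item 2 (Procedures), "The MISC/WTM training will be led by 10 women leaders in the Kahemba community". The same item says that these women differ from the WTM-only trainers. Item 13.D (Consent Process) adds that each gives biweekly home sessions to the mothers assigned to her. For the other arm, "Twenty women with leadership and communication skills have already been trained and are implementing WTM in the R01 trial", and they are to train the WTM-only households of this study as well. Caseloads are not stated for either arm. Nor is it stated whether all twenty women will serve the 34 WTM-only households.

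**Randomisation.** Items 2, 12.A and 12.B make the village the randomised unit. The number of villages and the number of households per village are not given.

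**Precision.** Item 9.B.iii gives the inputs and results:
- "With n=66 in MISC+WTM arm and n=34 in WTM only arm"
- "we expect an over 90% retention rate for the full year"
- "the unadjusted effect size of 0.60 is detectable as statistically significant with power of 0.80 and 0.05 level of significance in two-tailed tests"
- for the adjusted analysis, "two repeated measures at 6 and 12 months with the planned covariance adjustment for baseline"
- "Assuming correlation of 0.4 between pairs of repeated measures seen in past testing of MISC"
- "the adjusted detectable effect size is 0.44"

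It then concludes that no meaningful arm difference will be missed at this sample size. It mentions no ICC, design effect, village count or trainer term.

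**The concern.** Mothers taught at home by the same woman for a year are likely to have correlated outcomes, and so are households in one village. The 0.4 in item 9.B.iii is the correlation between repeated measures on the same subject, so it accounts for neither source. Trainers work in one arm only, which makes between-trainer variation part of the error of the arm contrast. Village variation enters in the same way because whole villages are allocated.

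If the planning figure leaves both out, the trial can detect only larger differences than it states. The item also says that the estimated effect size will be used to power later trials, so overstated precision would carry forward. If the final analysis made the same omission, its confidence intervals would be too narrow, and a few strong trainers could pass for an effect of MISC.

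**Working it through.** **Inputs from the protocol.** 66 and 34 households; retention of 90%, giving 59.4 and 30.6 analysed; two-sided alpha 0.05; power 0.80; repeated-measures correlation 0.4; 10 MISC trainers; 20 WTM-only trainers.

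**Assumptions, not in the protocol.** Trainer ICC of 0.02, 0.05 or 0.10, taken on the scale of the outcome analysed; households spread evenly over trainers; all twenty WTM-only trainers in use, unless stated otherwise.

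**Step 1: reproduce the plan's figures.** For independent households, the detectable effect is (1.960 + 0.842) × sqrt(1/n1 + 1/n2).
- At 66 and 34: 2.802 × sqrt(0.01515 + 0.02941) = 2.802 × 0.2111 = 0.591, or 0.597 with the t distribution. This matches 0.60.
- At 59.4 and 30.6: 2.802 × 0.2225 = 0.623. The printed 0.60 therefore fits full enrolment better than the stated retention. That is a separate matter.
- Adjusted: the factor for the mean of two follow-up measures with baseline as covariate is sqrt[(1 + 0.4)/2 − 0.4²] = sqrt(0.54) = 0.735, and 0.60 × 0.735 = 0.441. This matches 0.44.

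The independence formula accounts for both figures, which leaves no room for a design effect.

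**Step 2: average trainer loads.** MISC 66/10 = 6.6, or 5.94 at 90% retention. WTM-only 34/20 = 1.7, or 1.53 at 90% retention, on the assumption above.

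**Step 3: add a trainer ICC.** In each arm DE = 1 + (households per trainer − 1) × ICC. The SE ratio is sqrt[(DE1/n1 + DE2/n2) / (1/n1 + 1/n2)]. At 90% retention:

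| Trainer ICC (assumed) | DE, MISC | DE, WTM-only | SE ratio | 0.44 × ratio |
|---|---|---|---|---|
| 0.02 | 1.099 | 1.011 | 1.020 | 0.45 |
| 0.05 | 1.247 | 1.026 | 1.050 | 0.46 |
| 0.10 | 1.494 | 1.053 | 1.097 | 0.48 |

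As an example, at ICC 0.05: 1.247/59.4 + 1.026/30.6 = 0.0545; sqrt(0.0545) = 0.2335; 0.2335/0.2225 = 1.05.

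Starting from the 90%-retention figure instead of 0.44 (0.623 × 0.735 = 0.458), the adjusted values are 0.467, 0.481 and 0.502.

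The increase is modest because the smaller arm carries about two thirds of the variance, 0.02941/(0.01515 + 0.02941) = 0.66, and at 1.7 households per trainer it is almost unclustered.

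**Step 4: sensitivity to the WTM-only load.** If only five of the twenty women served this arm (34/5 = 6.8 each), then at full enrolment:
- ICC 0.05: DEs 1.28 and 1.29, SE ratio 1.134.
- ICC 0.10: DEs 1.56 and 1.58, SE ratio 1.254.

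**Step 5: village level, illustration only.** With an assumed 10 analysed households per village and a village ICC of 0.05, DE = 1 + 9 × 0.05 = 1.45 in both arms, and the unadjusted 0.623 becomes 0.623 × sqrt(1.45) = 0.75. This could outweigh the trainer effect.

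**Step 6: type I error if the analysis ignored trainers.** 2 × [1 − Φ(1.96/ratio)] with the ratios in Step 3 gives 0.055, 0.062 and 0.074.

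**The case against.** **No analysis model is stated.** The protocol gives no standard error or variance method for the final comparison; it mentions only two follow-up measures with baseline adjustment. A reader might infer that the trial's standard errors will be too small and its type I error above 5%. The documents do not support that, because they do not say that the analysis will ignore clustering. The Step 6 figures are therefore conditional. This part of the objection stands.

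**The loads are averages.** A reader might also take 6.6 against 1.7 as the actual caseloads. The 1.7 holds only if all twenty women are used equally, which is not stated, and with five women the contrast between arms disappears. This stands too, but Step 4 shows that fewer trainers make the loss of precision larger.

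**A village term may be enough.** If each trainer stays in one village, a village random intercept covers the trainer level. No passage says whether trainers cross villages. That decides whether a separate trainer term is needed. It does not rescue the planning figures, which include no village term either.

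**The study is exploratory and has fidelity controls.** The sample was set by timeline and resources, and monthly video review with expert supervision should limit differences between trainers. This argues for a small ICC, not for zero. The exploratory label also sits poorly beside the assurance that every meaningful difference will be found.

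**Conclusion.** The stated detectable effects of 0.60 and 0.44 assume independent households, and the design does not provide independence. Any positive village or trainer ICC makes them too favourable.

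For the trainer level alone, the true standard error is about 2% to 10% larger than under independence, and 0.44 becomes about 0.45 to 0.48. This rests on assumed ICCs of 0.02 to 0.10, even loads, twenty active WTM-only trainers and 90% retention. With five WTM-only trainers at full enrolment, the increase is about 13% at ICC 0.05 and 25% at ICC 0.10. Village clustering adds to this by an amount that cannot be fixed without the number of villages.

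An inflated type I error is not established; it would follow only if the unstated final model also left the clustering out. The point is worth correcting because the change is cheap and the text promises more than the design delivers, but the trainer effect by itself is modest.

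**What to change.** 1. Record the trainer ID and village of every household. State the number of villages, the trainer caseloads in both arms, and whether any trainer works in more than one village.
2. Restate the detectable effects over a range of ICCs, using DE1/n1 + DE2/n2 with arm-specific design effects and the retained sample sizes. Where trainers cross villages, include both the village and the trainer component, because they add.
3. Withdraw the statement that any meaningful difference will be found.
4. Prespecify the analysis: a village random intercept, plus a trainer random intercept where trainers span villages, with small-cluster degrees of freedom. At about 1.7 households per trainer, the trainer variance in the WTM-only arm may not be estimable, so name a simpler structure for that arm in advance.
5. Acknowledge the limit of the model. Because trainers are wholly nested in arm, it corrects the error bars but cannot separate trainer skill from MISC itself.

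The cost is one recorded variable, one model term and a less favourable stated figure.

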### **3. Subject Population.**

#### **A. Describe the subject population.**

We will study 100 non-konzo mother/child dyads, and all household children 12 to 48 months of age. 34 mother/child pairs will receive 12-months of biweekly home-based personalized training sessions with wetting method (WTM) training only to detoxify cassava flour in the prevention of konzo, and 66 dyads will receive 12 months of MISC caregiver training to improve early childhood development (ECD) combined with WTM. These families represent a homogenous population of Congolese people living in the Kahemba district of the Bandundu Province, Democratic Republic of Congo (DRC) in southwestern Bandundu province. People in this rural district depend heavily on daily cassava root and leaves for food and cash income. A typical population of 100,000 cultivates about 5000 hectares of cassava per year. Traditional varieties of cassava, which are subject to the cassava mosaic virus, yield around 6 tons/hectare per year. Crop losses in the 1990s ranged from 5% to 95%, thereby resulting in severe food insecurity. Cassava dependency resulted in up to 5% of individuals in affected villages developing walking difficulties typical of konzo. A substantially larger percentage (estimated up to 10%) has neurological signs and symptoms of an earlier stage of konzo in which ambulatory difficulty is not overt. Our recent findings suggest that deficits in cognition may also be part of neurological picture. Therefore, this is an at-risk population.

